12.2 Laboratory Tests

Safety labs are performed at Screening and on post-operative Day 3, and post-operative Day 7 (if subject is still hospitalized). For hematology, chemistry, and coagulation, summary statistics (n, mean, SD, minimum, median, and maximum) will be presented for the observed values at each time point for the safety population. Summary statistics will also be presented for the change from baseline values to each post-baseline time point. In these displays, baseline will be defined as the last values obtained prior to the first dose.

Pregnancy tests are performed at Screening and before each surgery.

For all tests, including pregnancy tests, results will be displayed in subject listings for the safety population. Laboratory reference ranges will be provided by the laboratory site and will be included in an appendix of the clinical study report.

12.3 Physical Examinations

Complete physical examinations are performed from Screening through post-operative Day 14 (or for as long as the patient remains hospitalized), at hospital discharge, and at the second surgery (if applicable). Each physical examination includes weight measurements and lower extremity assessments to identify any clinical symptoms of venous thromboembolism (VTE). Height is measured at the Screening visit only.

A frequency table of lower extremity assessment findings will be presented by treatment group for the safety population.

All physical exam and lower extremity assessment findings will be displayed in subject listings for the safety population.

12.4 Vital Signs

Vital signs will be collected daily from Screening through post-operative Day 14 (or for as long as the patient remains hospitalized), at hospital discharge, and at the second surgery. Summary statistics (n, mean, SD, minimum, median, and maximum) will be presented for the observed values at each time point for systolic and diastolic blood pressure, heart rate, respiratory rate, oxygen saturation, and temperature at each time point for the safety population. Summary statistics will also be presented for the change from baseline values to each post-baseline time point. In these displays, baseline will be defined as the last value obtained prior to the first dose.

All vital signs results will be displayed in subject listings for the safety population.

13 SUBJECT LISTINGS

All data that are collected and entered into the study database will be presented in subject listings.

14 INTERIM ANALYSES

An interim analysis of limited efficacy, safety, and tolerability was proposed in the initial study protocol. The purpose of the interim analysis was to allow for sample size adjustment based on observed data, e.g., an increase in sample size, if needed. An interim analysis with primary endpoints return of bowel function (GI2) and LOS (Discharge Order Written) was performed in the spring of 2020. Efficacy and safety tables were provided to the sponsor in May of 2020.

The change in primary endpoint with Protocol Amendment #5 modified the emphasis of this study. No change in sample size was made because the endpoints reviewed were no longer the primary endpoints. As previously discussed in Section 4.1, the subjects used for this analysis are now included only in the safety population.

15 APPENDIX A

MME Calculator Guidance

1. Determine the total daily amount of each opioid the subject takes
2. Convert each to MMEs by multiplying the dose for each opioid by the conversion factor (see table below)
3. Add them together

Use the formula: Strength per unit (*units in table below*) X (number of units/day) X MME factor = MME/day

Example for Hydrocodone 5/325, 2 units BID: 5mg X 4 X 1 = 20 MME/day

Type of Opioid (strength units)	MME Conversion Factor
Buprenorphine film/tablet ⁱⁱⁱ (mg)	
Buprenorphine ⁱⁱⁱ (mcg/hr)	
Buprenorphine ⁱⁱⁱ (mcg)	
Butorphanol (mg)	7
Codeine (mg)	0.15
Dihydrocodeine (mg)	0.25
Fentanyl buccal or SL tablets, or lozenge/troche ^{iv} (mcg)	0.13
Fentanyl film or oral spray ^v (mcg)	0.18
Fentanyl nasal spray ^{vi} (mcg)	0.16
Fentanyl patch ^{vii} (mcg)	7.2
Hydrocodone (mg)	1
Hydromorphone (mg)	4
Levorphanol tartrate (mg)	11
Meperidine hydrochloride (mg)	0.1
Methadone ^{viii} (mg)	3
>0, ≤20	4
>20, ≤40	8
>40, ≤60	10
>60	12
Morphine (mg)	1
Opium (mg)	1
Oxycondone (mg)	1.5
Oxymorphone (mg)	3
Pentazocine (mg)	0.37
Tapentadol ^{ix} (mg)	0.4
Tramadol (mg)	0.1

i The MME conversion factor is intended only for analytic purposes where prescription data are used to calculate daily MME. Use the formula: Strength per Unit X (Number of Units/ Days

Supply) X MME conversion factor = MME/Day. This value does not constitute clinical guidance or recommendations for converting patients from one form of opioid analgesic to another. Please consult the manufacturer's full prescribing information for such guidance. Use of this file for the purposes of any clinical decision-making warrants caution. This is particularly true with regard to methadone (see viii below).

ii National Center for Injury Prevention and Control. CDC compilation of benzodiazepines, muscle relaxants, stimulants, zolpidem, and opioid analgesics with oral morphine milligram equivalent conversion factors, 2017 version. Atlanta, GA: Centers for Disease Control and Prevention; Available at <https://www.cdc.gov/drugoverdose/resources/data.html> . For more information, send an email to [contact]" [contact].

iii Buprenorphine products are listed but do not have an associated MME conversion factor. These buprenorphine products, as partial opioid agonists, are not expected to be associated with overdose risk in the same dose-dependent manner as doses for full agonist opioids. The conversion factors for drugs prescribed or provided as part of medication-assisted treatment for opioid use disorder should not be used to benchmark against dosage thresholds meant for opioids prescribed for pain.

iv The MME conversion factor for fentanyl buccal tablets, sublingual tablets, and lozenges/troche is 0.13. This conversion factor should be multiplied by the number of micrograms in a given tablet or lozenge/troche.

v The MME conversion factor for fentanyl film and oral spray is 0.18. This reflects a 40% greater bioavailability for films compared to lozenges/tablets and 38% greater bioavailability for oral sprays compared to lozenges/tablets.

vi The MME conversion factor for fentanyl nasal spray is 0.16, which reflects a 20% greater bioavailability for sprays compared to lozenges/tablets.

vii The MME conversion factor for fentanyl patches is based on the assumption that one milligram of parenteral fentanyl is equivalent to 100 milligrams of oral morphine and that one patch delivers the dispensed micrograms per hour over a 24 hour day. Example: 25 ug/hr fentanyl patch X 24 hrs = 600 ug/day fentanyl = 60 mg/day oral morphine milligram equivalent. In other words, the conversion factor not accounting for days of use would be 60/25 or 2.4. However, since the fentanyl patch remains in place for 3 days, we have multiplied the conversion factor by 3 (2.4 X 3 = 7.2). In this example, MME/day for ten 25 μ g/hr fentanyl patches dispensed for use over 30 days would work out as follows: Example: 25 ug/hr fentanyl patch X (10 patches/30 days) X 7.2 = 60 MME/day. Please note that because this allowance has been made based on the typical dosage of one fentanyl patch per 3 days, you should first change all Days Supply in your prescription data to follow this standard, i.e., Days Supply for fentanyl patches= # of patches X 3.

viii The CDC MME conversion factor to calculate morphine milligram equivalents of methadone is 3. Calculating MME for methadone in clinical practice often involves a sliding-scale approach whereby the conversion factor increases with increasing dose since the conversion factor of 3 for methadone could underestimate MME for a given patient. CMS uses this conversion factor when analyzing Medicare population opioid use. CMS uses the graduated methadone MME conversion factors to calculate MME within the Overutilization Monitoring System (OMS) for identifying

and reporting potential opioid overutilizers.

https://www.cdc.gov/drugoverdose/pdf/calculating_total_daily_dose-a.pdf.

ix Tapentadol is a mu receptor agonist and norepinephrine reuptake inhibitor. Oral MMEs are based on degree of mu receptor agonist activity, but it is unknown if this drug is associated with overdose in the same dose-dependent manner as observed with medications that are solely mu receptor agonists.

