6.14. Hospital Discharge

Subjects may not be discharged until all of the following criteria are met:

- Passage of stool
- Ability to tolerate solid food and drink comfortably
- Adequate oral analgesia
- Subject's willingness to be discharged.

Information related to Hospital Discharge after the first bowel resection will be recorded during the Post-Surgical period as:

- When discharge order is written (date and time)
- When subject departs from the hospital (date and time)

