11.3 Exploratory Endpoints

The exploratory endpoints are:

- Hospital LOS (number of days in the hospital, evaluated in hours) will be measured first by time to discharge order is written. The time will start at time of surgical closure and run until discharge order is written.
- Pain values, evaluated using
 - Values recorded from the NPRS
 - Analgesia consumption, including totals for opioid use and morphine equivalents
 - See Section 15 APPENDIX A for conversion guidelines
- The number of subjects with recorded bowel obstructions (Listing only)
 - AE Preferred Terms having the phrase "bowel obstruction" in them e.g., small bowel obstruction
- The number of subjects with a hospital re-admission
- Blood product transfusion volume on the day of surgery (Listing only)

The following LOS parameters will also be evaluated:

- Time from surgical closure to actual discharge
- Time from surgical closure to standard discharge (Listing only) The time will start at time of surgical closure and run until all four criteria for discharge have been met. The criteria are:
 - Passage of stool
 - Ability to tolerate solid food and drink comfortably
 - Adequate oral analgesia, and
 - Subject's willingness to be discharged

Selected time-to-event endpoints (See Table in Section 11.5) will be analyzed using a stratified Cox PH model with treatment as the main effect, stratified by surgery type (laparotomy versus minimally invasive). Comparison of treatment groups and assessment of the significance of the

parameter estimates for surgery type will be made using the Wald chi-square test. In addition to the semi-parametric Cox PH model, non-parametric Kaplan-Meier survival curves will be produced for the two treatment groups and compared using a stratified log-rank test. The number of hours to each endpoint will be presented in summary tables with descriptive statistics for the mITT and PP populations.

Pain assessments will be collected daily from surgery (Day 0) through post-operative Day 14 (or for as long as the patient remains hospitalized), at hospital discharge, and at the second surgery.

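### SAP Appendix A has no conversion for parenteral opioids, so morphine-equivalent totals are misconverted for any subject given a parenteral opioid whose equivalence differs from the listed factor

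*SAP*

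**What the plan says.** SAP section 11.3 lists, among the exploratory pain endpoints, "Analgesia consumption, including totals for opioid use and morphine equivalents" and sends the analyst to Appendix A. Continuous exploratory endpoints are compared between arms by the van Elteren test.

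Appendix A instructs the analyst to "Convert each to MMEs by multiplying the dose for each opioid by the conversion factor" and then add the results; its formula is strength times "number of units/day) X MME factor = MME/day". Morphine (factor 1) and hydromorphone (factor 4) have one row each, with no route given. Fentanyl has rows for buccal, sublingual or lozenge products (0.13 per mcg), film or oral spray (0.18), nasal spray (0.16) and patch (7.2), but none for intravenous, epidural or patient-controlled use.

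The footnotes to the table set its scope:
- Footnote ii names the source as a compilation of "opioid analgesics with oral morphine milligram equivalent conversion factors".
- Footnote i says: "The MME conversion factor is intended only for analytic purposes where prescription data are used to calculate daily MME".
- Footnote vii, in deriving the patch factor, assumes that "one milligram of parenteral fentanyl is equivalent to 100 milligrams of oral morphine".
- Footnote viii says: "The CDC MME conversion factor to calculate morphine milligram equivalents of methadone is 3".

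The data to be converted are of another kind. Protocol 6.11 collects opioid use daily from Screening to Day 14 or discharge, and 6.9 records perioperative opioids. Protocol 5.6 does not list parenteral opioids among the prohibited treatments and otherwise leaves concomitant therapy unrestricted. Protocol 6.14 makes "Adequate oral analgesia" a condition of discharge.

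**The concern.** The table was built for one kind of data (dispensed, mostly oral products) and is applied to another (opioids given around and after major abdominal surgery). For a parenteral dose the appendix offers either a factor derived for the oral route or no factor at all. This is more than missing detail: the instruction to multiply each dose by its listed factor, followed literally, gives a wrong number whenever the parenteral equivalence differs from that factor.

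The error need not be the same in both arms. Protocol 1.4 states the hypothesis that LB1148 shortens the time to return of normal GI function. If that also brings forward the change from parenteral to oral opioid, a conversion that ignores route could create or hide a difference in morphine equivalents with no difference in true use.

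**Working it through.** **1. The SAP's own examples.** Hydrocodone: 5 mg x 4 x 1 = 20 MME/day, as stated. Patch: 25 x (10/30) x 7.2 = 60 MME/day, as stated. The arithmetic is sound for the products the table covers.

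**2. Parenteral fentanyl, from the SAP alone.** Footnote vii gives 1 mg parenteral = 100 mg oral morphine, so 100/1000 = 0.1 MME per mcg. For 100 mcg:

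| Treatment of the dose | MME | Against footnote vii |
|---|---|---|
| Footnote vii, 0.1 | 10 | reference |
| No row, so not counted | 0 | -100% |
| Buccal/sublingual/lozenge row, 0.13 | 13 | +30% |
| Nasal row, 0.16 | 16 | +60% |
| Film/oral spray row, 0.18 | 18 | +80% |

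**3. Parenteral morphine or hydromorphone.** The documents give no parenteral-to-oral ratio r. I assume r from 1 (no error) to 3. A parenteral day worth T oral MME is then recorded as T/r, an undercount of 1 - 1/r: 0% at r = 1, 50% at r = 2, 67% at r = 3.

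**4. How this could differ by arm (illustration only).** Assume identical true use in both arms, 60 oral MME/day for 5 days (300 in total), with a switch to oral after day 2 in one arm and after day 3 in the other. None of these inputs is in the documents. With k parenteral days, recorded total = k x 60/r + (5 - k) x 60.

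| r | Switch after day 2 | Switch after day 3 | Ratio |
|---|---|---|---|
| 1 | 300 | 300 | 1.00 |
| 2 | 2 x 30 + 3 x 60 = 240 | 3 x 30 + 2 x 60 = 210 | 1.14 |
| 2.5 | 2 x 24 + 3 x 60 = 228 | 3 x 24 + 2 x 60 = 192 | 1.19 |
| 3 | 2 x 20 + 3 x 60 = 220 | 3 x 20 + 2 x 60 = 180 | 1.22 |

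Now let the parenteral drug be fentanyl, 600 mcg/day (600 x 0.1 = 60 MME), with factor f applied: k x 600 x f + (5 - k) x 60.
- f = 0 (not counted): 180 against 120; the earlier-switching arm looks higher.
- f = 0.13: 336 against 354; it looks lower.
- f = 0.18: 396 against 444; it looks lower still.
- f = 0.1: 300 against 300.

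The sign therefore depends on the opioid and on how the analyst fills the gap. If the arms switch at the same time, the between-arm part disappears.

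**5. Patch row.** Footnote vii takes one patch as lasting 3 days, so units/day = 1/3 and 25 x 1/3 x 7.2 = 60, which matches its worked result. Only counting a worn patch as a new unit every day would give 25 x 1 x 7.2 = 180.

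**6. Methadone rows.** The table lists a flat 3 and a graduated 4 to 12. At 40 mg/day these give 40 x 3 = 120 or 40 x 8 = 320.

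**The case against.** The strongest reply is that the documents never show how much parenteral opioid is given, when subjects change route, or that the arms differ. The discharge criterion does not date the switch. The 14% to 22% figure needs an assumed ratio, dose, duration and pair of switch days, and all parenteral use must be morphine or hydromorphone. A reader might infer from it that the table biases the comparison against LB1148. The documents do not support that: neither size nor direction can be fixed, and a shift in totals does not translate directly into a shift in a rank test. This part of the reply stands.

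The fentanyl rows are labelled by product, and nothing directs their use for parenteral doses. That is fair, but the alternative under the same rule is no factor, and the dose drops out of the total. It is also true that 0.1 per mcg appears only as a step in deriving the patch factor; it is nevertheless the one parenteral equivalence the SAP states.

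Two further readings are tempting and fail, in whole or in large part:
- That the patch factor contradicts the units-per-day formula. It does not, as step 5 shows.
- That the two methadone scales are equally applicable. Footnote viii gives 3 as the CDC factor, the appendix cites the CDC compilation as its source, and the graduated scale is tied to a CMS system for monitoring overuse. What is missing is one line saying which applies.

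Finally, the endpoint is exploratory, p-values are nominal, and the collected data will be listed, so totals could be recalculated later. This limits the importance of the point but does not make the rule correct.

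**Conclusion.** Wrong as written, and minor. Appendix A misconverts any parenteral opioid whose equivalence differs from the listed factor. For parenteral fentanyl this follows from the SAP's own figures: a complete loss, or an overstatement of 30% to 80%. For parenteral morphine and hydromorphone it rests on an assumed ratio: an undercount of 50% to 67% at a ratio of 2 to 3, and none at 1.

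Whether any subject is affected depends on parenteral use, which the inpatient setting and the absence of a restriction make plausible but which the documents do not quantify. A between-arm distortion is possible, not shown. The consequence is confined to the morphine-equivalent part of the exploratory pain endpoint; the primary adhesion analysis does not use it.

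**What to change.** Before unblinding for the final analysis:
- Make the analytic conversion in Appendix A specific to route. Use footnote vii's 0.1 MME per mcg for parenteral fentanyl, and take parenteral factors for the other opioids from one cited source.
- Where no such factor is available, report parenteral and oral totals separately by arm and do not add them. Show doses of unknown route apart, by arm, and leave them out of any sum.
- State that the flat methadone factor of 3 applies, or delete the graduated rows.
- Leave the patch factor as it is; at most, note that patches are counted as applied and not per day worn.

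The table and program changes are small. The real condition is that opioid route can be obtained from the eCRF or source records. Protocol 5.6, 6.5 and 6.11 ask for dates, reasons and daily use but do not mention route, so the sponsor should confirm this first. If route was not captured, retrieving it from source records is added work for the sites.

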17 REVISIONS TO STATISTICAL ANALYSIS PLAN

Date	Revision
October 11, 2022	Version 2.0: Extensive revisions reflect the changes made to the study protocol covering Amendments 4, 5, and 6. The most significant change was the in the designation of the primary endpoint. The primary endpoint was changed from the number of hours from surgical closure to return of GI function as measured by GI2 to compare the change from baseline in extent and severity of intra-abdominal adhesions among subjects treated with LB1148 or placebo. Another significant change increased the alpha to 0.10 and changed the CIs from 95% to 90%.
March 10, 2023	Version 3.0: The following statement was returned to this version of the SAP. “All statistical tests will be 2-sided, with p-values considered nominal. A p-value < 0.05 will be highlighted.” Gender and BMI added to models in specific efficacy analyses. An analysis was added regarding time between drug administration and actual surgery start time and efficacy between the two treatment groups. Confidence intervals were changed from 90% back to 95% throughout. Cocclini scoring system added to the primary endpoint. One shift table was added to better display the change in number of adhesions between the two surgeries.
